### **11.2.4. Disease-Related Events and/or Disease-Related Outcomes Not Qualifying as AEs or SAEs**

Oral mucositis will not be reported as an AE as it is captured as a study endpoint in the CRF. Progressive disease found by scan or on clinical evaluation should be captured on the applicable CRF pages and not recorded as an AE.

### **11.2.5. Grading of Adverse Events**

The severity of adverse events will be designated as mild, moderate, severe, life threatening, or fatal per NCI CTCAE version 5.0. If not specifically addressed in NCI CTCAE version 5.0, use [Table 4](#) below:

**Table 4: Adverse Event Severity**

Grade	Criteria 
Mild – Grade 1	Asymptomatic or mild symptoms; clinical or diagnostic observations only; intervention not indicated
Moderate – Grade 2	Minimal, local, or noninvasive intervention indicated; limiting age-appropriate instrumental ADL 
Severe – Grade 3	Severe or medically significant but not immediately life-threatening; hospitalization or prolongation of hospitalization indicated; disabling; limiting self-care ADL 
Life Threatening – Grade 4	Life-threatening consequences; urgent intervention indicated
Death – Grade 5	Death related to adverse event

 A semi-colon indicates ‘or’ within the description of the grade.

 Instrumental ADL refer to preparing meals, shopping for groceries or clothes, using the telephone, managing money, etc.

 Self-care ADL refer to bathing, dressing and undressing, feeding self, using the toilet, taking medications, and not bedridden.

### 11.3. Relationship to Study Drug

All AEs will be categorized by the Investigator with respect to their relationship to GC4419. The Investigator should consult the current IB and/or product information in the determination of his/her assessment. The relationship between GC4419 and the AE may be considered related, possibly related, or unrelated. The criteria for each category are listed below:

- **Related:** It is likely that GC4419 caused or contributed to the cause of the adverse event or laboratory abnormality, when the temporal sequence from the time of GC4419 administration, the known consequences of the subject’s clinical/state condition or study procedures, the effects of discontinuing or reintroducing GC4419 on the adverse event, and other medically relevant factors are considered.
- **Possibly Related:** There is a reasonable possibility that the adverse event or laboratory abnormality was caused by GC4419, when the temporal sequence from the time of GC4419 administration, the known consequences of the subject’s clinical state/condition or study procedures, and other medically relevant factors are considered.
- **Unrelated:** The Investigator has a high level of certainty that the subject’s clinical state/condition, study procedures, or other medically relevant factors other than treatment with GC4419 caused the adverse event or laboratory abnormality. This relationship category should only be used when a clear precipitating cause exists and it is not reasonably possible that the event is caused by treatment with GC4419.

If the relationship between the AE/SAE and the investigational product is determined to be “possibly related” the event will be considered to be related to the investigational product for the purposes of expedited regulatory reporting.

## **11.4. Recording Adverse Events**

All AEs must be recorded on the appropriate CRF regardless of the severity or relationship to GC4419. All AEs that meet the seriousness criteria should also be recorded on the SAE Report Form. All SAEs must be reported to the Sponsor or delegated organization within the timeline stated in [Section 11.2](#).

The recording of AEs will be based on data obtained from the following sources:

- Medical and surgical history
- Physical examinations including vital signs
- Clinical laboratory test results
- Subject verbal reports to the investigational staff and documented in the medical chart

All clinical events, including both observed (such as any reaction at sites of application) and volunteered problems, complaints, or symptoms, are to be recorded. The need to capture this information is not dependent upon whether the clinical event is associated with GC4419 use. AEs resulting from concurrent illnesses, reactions to concurrent medications or symptomatic progression of disease states, other than the disease under study, are also to be recorded.

The information to be recorded for AEs will include:

- The specific type of event in standard medical terminology – diagnosis if known, is preferred over symptoms
- Duration of the clinical event (start and stop dates)
- Severity (Grade 1, 2, 3, 4, or 5) of the clinical event
- Seriousness (SAE) criteria, if applicable
- Relationship of the AE to GC4419 as defined in [Section 11.3](#)
- Management of GC4419 administration and other action taken to alleviate the clinical events
- Clinical outcome of the AE

## **11.5. Follow-up of AEs and SAEs**

If an adverse event changes in severity grade between the date it was initially recorded through the 30-Day Follow-up Period, the event should be recorded as a new AE; however, only one SAE should be reported to the Safety vendor for the event with the highest severity grade recorded.

After the initial AE/SAE report, the Investigator is required to proactively follow each subject and provide further information on the subject's condition. The Investigator will ensure that follow-up includes any supplemental investigations as may be indicated to elucidate the nature and/or causality of the AE or SAE. This may include additional laboratory tests or investigations, histopathological examinations, or consultation with other health care professionals.

Non-serious AEs that have not resolved within 30 days after last dose of GC4419 will be considered ongoing, and marked as such in the CRF. All SAEs will be followed until they resolve or a new baseline is established, at which point the appropriate CRF page(s) or SAE Report Form(s) will be updated.

Routine collection of AEs will stop 30 days after last dose of GC4419, IMRT, or cisplatin (i.e., whichever occurs last); however, collection of clinical data will continue on events of interest or as clinical circumstances warrant that exceed the 30 days after last dose of GC4419, per below and described in other sections of the Protocol:

- OM: 4 weeks post last IMRT dose ([Section 10.7.3.1](#))
- Medical events which in the opinion of the Investigator, serious and are believed to be a result of study participation to warrant notifying the Sponsor ([Section 11.6](#) and [Section 11.8](#)). In these circumstances, the Investigator should contact the Galera Medical Monitor (or designee) directly to discuss the case, and how it should be reported.

As reasonably requested by the Sponsor, the Investigator will perform or arrange for the conduct of supplemental measurements and/or evaluations to elucidate as fully as possible the nature and/or causality of the AE or SAE. If a subject dies during participation in the study or during a 30-Day Follow-Up Period, the Sponsor will be provided with a copy of any post-mortem findings, including histopathology.

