**Statistical methods:**

The primary objective of this study is to further assess the safety profile of GC4419, with efficacy objectives of cumulative incidence of SOM, days of SOM, and tumor outcome key secondary efficacy endpoints. No formal statistical hypothesis testing is prespecified for the primary safety objectives. A sample size of up to 70 subjects has been selected to obtain adequate safety and efficacy subject data to compare with observed data in North American studies and historical controls for IMRT with Cisplatin. These results will also contribute to pooled analysis of an overall minimum safety database of 300 subjects with head and neck cancer who will, across all studies of GC4419, have received a full course of GC4419 at the intended dose (90 mg), schedule (1-hour infusion, 5 days/week, prior to IMRT), and duration (single course of 6-7 weeks) in combination with concurrent IMRT and cisplatin. The overall safety database size of 300 will allow for detection with 95% probability of adverse events of 1% true incidence in at least 1 subject.

As this is the first study of this drug in EU, the efficacy analysis will allow for comparison to North American results and historical controls and confirm uniformity in applying OM scoring procedures used for WHO criteria that could be used to inform future development programs.

Safety and efficacy will be assessed on an "intent to treat" (ITT) population consisting of all enrolled subjects who receive at least one dose of GC4419, and on a "per protocol" population consisting of subjects who receive at least 60 Gy of IMRT and at least 5 weeks (25 doses) of GC4419. Overall rates of adverse events, serious adverse events, and SOM/Grade 4 OM incidence will be summarized descriptively.

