### 5.2. Endpoints

#### Primary Endpoint:

- Frequency, duration, and severity of AEs and serious AEs (SAEs);
- Incidence and shifts of clinically significant laboratory abnormalities

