### **12.4. Safety Analysis**

AEs will be grouped by system organ class, high level term, and preferred term according to the Medical Dictionary for Regulatory Activities (MedDRA) dictionary. Incidence by subject will be tabulated for all treatment-emergent, serious, severe, and treatment-related adverse events. Detailed listings will be provided for all serious adverse events, deaths, and withdrawals due to adverse events.

Laboratory measurements and vital signs will be summarized by treatment group at each of the protocol-specified time points.

Safety parameters will be summarized with descriptive statistics on the safety population, defined as the ITT population; viz., all subjects who received at least one dose of GC4419.

Further details will be provided in the study's Statistical Analysis Plan.

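### Recording every grade change as a new AE splits AE duration, a named part of the primary endpoint, and no rule rejoins the pieces

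*Combined protocol and SAP*

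**What the plan says.** The first primary endpoint, in Section 5.2 and the synopsis, is "Frequency, duration, and severity of AEs and serious AEs (SAEs". Neither place says whether frequency counts subjects or events.

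Section 11.4 lists what is recorded for each AE, including "Duration of the clinical event (start and stop dates".

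Section 11.5 sets the rule for an event whose grade moves: "If an adverse event changes in severity grade between the date it was initially recorded through the 30-Day Follow-up Period", then "the event should be recorded as a new AE; however, only one SAE should be reported to the Safety vendor". The single SAE report is the one at the highest grade. The rule is not limited to worsening, so a fall in grade also opens a new record.

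On analysis, Section 12.4 says "Incidence by subject will be tabulated for all treatment-emergent, serious, severe, and treatment-related adverse events". It gives no method for summarizing AE duration, and adds "Further details will be provided in the study's Statistical Analysis Plan". The synopsis says "Overall rates of adverse events, serious adverse events, and SOM/Grade 4 OM incidence will be summarized descriptively", again without a unit. It also says "No formal statistical hypothesis testing is prespecified for the primary safety objectives".

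**The concern.** One clinical event that rises and falls in grade becomes several records, and the dates on each record cover only the time at that grade. Section 11.4 therefore asks for the duration of the event, while Section 11.5 has sites enter something else. If AE duration is summarized from the records as entered, it will be too short. In a safety study that is the unfavourable direction, because it makes toxicity look briefer than it was.

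Nothing in the text reviewed tells sites to link the records or tells the analysis to rejoin them. Safety is the primary objective of this single-arm study, and the synopsis intends its data for comparison with other studies and for a pooled database. A duration with an undefined unit would weaken both uses.

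**Working it through.** **What does not change.** The one safety figure the plan states is in Section 12.2: a database of 300 gives 95% probability of seeing, in at least one subject, an AE of 1% true incidence. It reproduces:

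1 − 0.99^300 = 0.951 (299 subjects is the smallest number that reaches 95%).

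This is a per-subject calculation, so the number of records each subject contributes does not enter it. By-subject incidence in Section 12.4 is likewise unchanged, since repeat records of one term in one subject count once. The maximum grade per subject can still be read from the split records.

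**What does change.** The documents give no AE counts, durations or rates of grade change, so the effect can only be expressed through assumptions. Let q be the share of episodes that change grade and c the number of changes in each of those. Assume records of one episode are contiguous.

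- Records = episodes × (1 + q·c).
- Total time is the same, so mean duration per record = mean episode duration ÷ (1 + q·c).

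| q (assumed) | c (assumed) | Record count, multiple of episodes | Mean duration per record, % of episode |
|---|---|---|---|
| 10% | 1 | 1.1 | 91% |
| 10% | 4 | 1.4 | 71% |
| 30% | 2 | 1.6 | 62.5% |
| 50% | 1 | 1.5 | 67% |
| 50% | 4 | 3.0 | 33% |

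**Illustration with assumed values.** Take 70 subjects, the planned maximum. Suppose 28 of them each have one 35-day episode of the same AE with two grade changes.

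- As recorded under Section 11.5: 28 × 3 = 84 records, with mean duration 35 ÷ 3 = 11.7 days.
- Rejoined: 28 episodes of 35 days.
- By-subject incidence: 28 ÷ 70 = 40% either way.

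**The case against.** The strongest reply is that Section 11.5 is a data-entry convention, not an analysis rule. Splitting by grade loses nothing: each segment keeps its onset, stop date and grade, and time at each grade is gained. Episodes can largely be rebuilt by merging adjacent records with the same term. Such derivations normally sit in the SAP. Section 12.1 refers to a separate SAP that takes precedence over the protocol, and it is not in the text reviewed, so it may already contain the rule.

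Much of this stands. The convention is usable, and nothing can be asserted about the separate SAP. However, without a link on the form, a merge has to infer from terms and dates whether adjacent records are one episode or two. That is a data-capture decision, and Section 11.5 is where sites receive their instruction.

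Several stronger readings are tempting but not supported:

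- **That the primary frequency is inflated.** The only AE tabulation specified is by subject. Inflation needs a count of records, which the undefined terms in Section 5.2 and the synopsis leave open but do not plan.
- **That AEs and SAEs are analysed in different units.** The single-SAE clause governs what is sent to the Safety vendor. What remains is reconciling several CRF records with one safety-database report.
- **That the distortion is very large.** A single event passing through five grade segments would give five records and a mean duration 80% too short, but no document figure says such a course is typical.
- **That all fluctuating toxicities are affected.** Section 11.2.3 keeps many low-grade laboratory changes out of the AE records, and Section 11.2.4 excludes oral mucositis.
- **That comparison with the other studies is compromised.** The documents do not describe how those studies record grade changes.

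**Conclusion.** The point holds for duration. If Section 11.5 is followed as written, each AE record gives time at one grade, and the text reviewed has no rule that turns those records into the event duration named in the primary endpoint. Under the assumed ranges above, mean duration per record would be between 91% and 33% of the true episode duration. The range depends on assumed rates of grade change and on durations being summarized record by record.

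For frequency, the finding is only that the unit is undefined. A count of records would be 1.1 to 3.0 times the number of episodes under the same assumptions, while a count of subjects would be unaffected. No hypothesis test is prespecified for safety, so no error rate is involved. The gap deserves correction, but it does not undermine the by-subject safety results.

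**What to change.** Keep the grade-change records, since they hold useful detail. Make two changes:

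1. In Section 11.5, add an episode identifier to the AE CRF so that sites link the records belonging to one clinical event.
2. In Section 12.4 and the SAP, state that AE frequency means the number of subjects with at least one event; that linked records count as one event at its maximum grade; and that duration runs from first onset to final resolution. The same text should say how episodes still marked as ongoing when collection ends are handled, because Section 11.5 allows non-serious events to stay open.

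The cost is one CRF field and a small amount of programming. No further data are needed from patients.

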### **10.7.3. Follow-up Phase**

#### **10.7.3.1. Post-IMRT OM Follow Up**

All subjects will be evaluated weekly ( $\pm$  2 calendar days) for the four weeks post-IMRT. At each visit, the following should be completed:

- Conduct OM assessment and record the severity using the WHO score
- Record AEs and concomitant medications through 30 days following the last dose of IMRT, cisplatin, or GC4419 (i.e., whichever occurs last)

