### **11.2.2. Collection Period for AEs and SAEs**

Any adverse medical condition or laboratory abnormality with an onset date prior to the date and time the subject received his/her first dose of study drug, GC4419, is considered pre-existing in nature and should be recorded as part of the subject's medical history. An adverse medical condition that begins on or after the first dose of study drug will be considered an adverse event, and will be considered an SAE if it meets serious criteria. AEs and SAEs will be followed for 30 days after the last dose of IMRT, cisplatin, or GC4419 (i.e., whichever occurs last), hereafter referred to as the "30-Day Follow-up Period". Similarly, new events will be reported as AEs/SAEs if the start date is within the 30-Day Follow-up Period. Increases in toxicity grade of pre-existing conditions that occur on or after the first study drug administration are also considered adverse events.

All adverse events must be recorded in the subject's source documents and on the CRF regardless of frequency, severity (grade) or assessed relationship to therapy. Additionally, SAEs must be submitted to the Safety vendor within 24 hours of awareness.

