AEs and SAEs with onset dates on or after the date of enrollment through 30 days following the last dose of GC4419, IMRT or cisplatin (i.e. whichever occurs last) will be recorded on the CRF. All subjects with SAEs will be followed until the events resolve, stabilize, become chronic, the subject completes the study, or the subject is lost to follow-up.

 Ventricular rate and P-R, QRS, QT, and QTc intervals will be assessed and recorded at Screening.

All OM assessments must be performed by trained evaluators. The extent of the subject's OM will be scored using the WHO OM toxicity scale. OM assessments will be completed at the Screening Visit, at the Baseline Visit, twice weekly (no less than two days apart) within each 5-day IMRT period and on the last day of IMRT or Early Termination Visit. For Week 1, the first OM assessment will occur at the Baseline Visit and one additional OM assessment must occur at least two days later during the week. The extent of the subject's OM will be scored using the WHO OM toxicity scale. OM assessments should continue weekly for four weeks following the last day of IMRT (Day 7, Day 14, Day 21 and Day 28  $\pm 2$  calendar days).

Symptom Related Questionnaires to be completed by subjects prior to the OM assessment at W1D1, and then prior to the second OM assessment each week and 28 days ( $\pm 2$  calendar days) post end of treatment (EOT).

For a woman of childbearing potential, serum pregnancy test must be performed at the Screening Visit and at the Last Day of IMRT or Early Termination Visit.

Clinical laboratory measurements will be conducted at the Screening Visit, twice during Week 1 (once at the Baseline Visit and again on Day 3, 4 or 5), and once weekly from Week 2 through the last day of IMRT. Clinical laboratory measurements at these visits will include the hematology profile (hemoglobin, hematocrit, red blood cell count, white blood cell count with differential, and platelet count. Differential to include total neutrophils, lymphocytes, monocytes, eosinophils, and basophils) and chemistry profile (glucose, BUN, creatinine, sodium, potassium, calcium, albumin, total protein, total bilirubin, direct bilirubin, alkaline phosphatase, ALT (SGPT), AST (SGOT), chloride, phosphate, bicarbonate, magnesium).

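### Section 11.5 marks non-serious AEs as ongoing on a GC4419-only clock that can run out before AE collection ends, so stop dates needed for AE duration can be lost

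*Combined protocol and SAP*

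**What the plan says.** Section 5.2 lists frequency, duration and severity of AEs and SAEs in the primary endpoint. Section 11.4 records duration through start and stop dates.

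Three places outside Section 11.5 set one collection window:

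- Section 11.2.2: "AEs and SAEs will be followed for 30 days after the last dose of IMRT, cisplatin, or GC4419", taking the latest of the three, and named there as the 30-Day Follow-up Period.
- Section 10.7.3.1: "Record AEs and concomitant medications through 30 days following the last dose of IMRT, cisplatin, or GC4419".
- Appendix 1, Table 5 footnote 10: "through 30 days following the last dose of GC4419, IMRT or cisplatin".

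Section 11.5 uses two clocks. On the longer clock it places grade changes ("between the date it was initially recorded through the 30-Day Follow-up Period"), the supply of post-mortem findings, and the end of routine collection ("Routine collection of AEs will stop 30 days after last dose of GC4419, IMRT, or cisplatin"). On a GC4419-only clock it places the CRF status of open events ("Non-serious AEs that have not resolved within 30 days after last dose of GC4419 will be considered ongoing"). The second half of the routine-collection sentence also refers to further data "as clinical circumstances warrant that exceed the 30 days after last dose of GC4419".

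SAEs are handled separately: "All SAEs will be followed until they resolve or a new baseline is established".

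**The concern.** The two clocks agree only if GC4419 is the last treatment given or ends on the same day as the last one. The protocol plans for cases where it does not. Section 9.1 takes subjects off GC4419 after two dose reductions but keeps them on cisplatin/IMRT and study assessments. Section 7.6 asks that subjects who stop because of an AE stay in follow-up.

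For these subjects, sites have two instructions for a non-serious AE that resolves between the dates. One site can enter a stop date and another can leave the event as ongoing, and both can point to Section 11.5. A stop date that was never entered cannot be restored by an analysis rule, so the duration is missing or is cut at the earlier date. The subjects exposed include those who stopped GC4419 for toxicity, in a study whose primary objective is safety.

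**Working it through.** The plan gives no figure of its own here, so the check is a comparison of the rules followed by a calendar calculation.

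**1. Literal reading of the rules between the two dates**

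| Event between the two dates | Rule | Result |
|---|---|---|
| New AE starts | 11.2.2 | Reportable |
| Open AE changes grade | 11.5, longer clock | Recorded as a new AE |
| Open non-serious AE resolves | 11.2.2, 10.7.3.1 | Followed and recorded, so a stop date exists |
| Same event | 11.5, GC4419-only clock | Already marked ongoing |

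A fall from Grade 2 to Grade 1 is therefore recordable in the gap, while the CRF rule has already fixed full resolution as ongoing. An AE that starts in the gap is reportable but could never have met the earlier cut-off.

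**2. Inputs**

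- Table 2: five doses a week, Monday to Friday, from Day 1, so dose *k* falls on Day 7 × floor((*k* − 1)/5) + ((*k* − 1) mod 5) + 1. For *k* = 35 this is 7 × 6 + 4 + 1 = 47, as in Table 2.
- Table 5 footnote 2: follow-up visits 7, 14, 21 and 28 days after the last IMRT day, each ±2 days.
- Earlier cut-off = last GC4419 day + 30. Later cut-off = last IMRT day + 30, assuming an uninterrupted course and no cisplatin after IMRT. Gap = later − earlier.

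**3. IMRT to Day 47 (35 fractions)**

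The later cut-off is 47 + 30 = Day 77. Visits fall on Days 54, 61, 68 and 75 (windows 52–56, 59–63, 66–70 and 73–77).

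| Last GC4419 dose | Day | Earlier cut-off | Gap (days) | Visits after earlier cut-off |
|---|---|---|---|---|
| 10 | 12 | 42 | 77 − 42 = 35 | 4 |
| 20 | 26 | 56 | 77 − 56 = 21 | 3 |
| 25 | 33 | 63 | 77 − 63 = 14 | 2 |
| 30 | 40 | 70 | 77 − 70 = 7 | 1 |
| 35 | 47 | 77 | 0 | 0 |

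The ±2-day windows do not change the visit counts. In the first row the earlier cut-off comes 47 − 42 = 5 days before IMRT ends.

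**4. Other course lengths**

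- 60 Gy at 2.0 Gy is 60/2.0 = 30 fractions, ending on Day 40, with a later cut-off of Day 70. Last doses on Days 12, 26, 33 and 40 give gaps of 28, 14, 7 and 0 days.
- 72 Gy at 2.0 Gy is 72/2.0 = 36 fractions against a maximum of 35 GC4419 doses. Fraction 36 falls on Day 50, so a gap of 50 − 47 = 3 days arises with no discontinuation at all.

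**5. Scale**

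The assumed 10–20% early discontinuation gives 70 × 0.10 = 7 to 70 × 0.20 = 14 subjects. This shows scale only; it is neither a count of affected subjects nor a ceiling. Section 7 sets the threshold at 5 or more weeks and Section 12.2 at 6 weeks. A Day 33 stop is early under Section 12.2 but not Section 7. A Day 40 stop is early under neither, yet has a 7-day gap if IMRT runs to Day 47. Only subjects with a non-serious AE still open past the earlier date are affected.

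**The case against.** The strongest reply is that the rule sets a status and does not forbid a later stop date. Sections 11.2.2 and 10.7.3.1 keep AE recording open to the later date, and Section 11.5 tells the investigator to follow each subject proactively. A diligent site would see the resolution and could enter it, and source documents allow many missing dates to be retrieved by query. This stands as a limit: the loss is possible, not certain. It does not remove the conflict, because Section 11.5 gives an explicit instruction to update the CRF on resolution only for SAEs.

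Second, no stated analysis is shown to be affected. Section 12.4 specifies incidence tabulations and listings and defines no duration summary; detail is left to a separate SAP whose text was not supplied. That is correct, so the effect on any particular table cannot be stated. Duration is nevertheless a named component of the primary endpoint.

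Third, the size depends on the course. A 30-fraction course gives shorter gaps, as shown above. The 10–20% also covers discontinuation for any reason, and subjects who leave the study entirely provide no further data (Section 8.9), so neither clock matters for them. Both points stand.

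Fourth, the second GC4419-only phrase introduces the later collection of OM and certain serious events and sets no cut-off for non-serious AEs, and the post-mortem sentence is not an AE follow-up rule. Also correct: aligning that phrase is mainly editorial. The conflict rests on the ongoing rule.

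**Conclusion.** The concern holds. Section 11.5 contradicts Section 11.2.2 and its own routine-collection sentence on the date to which non-serious AEs are followed, and nothing in the text presents the shorter window as deliberate. Read literally, it leaves some resolved AEs without a stop date in subjects whose GC4419 ends before their chemoradiation.

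The consequence is confined to duration and resolution status of non-serious AEs. SAE follow-up, by-subject incidence and maximum grade do not change. The gap figures assume an uninterrupted Monday-to-Friday course. After GC4419 has stopped, a break in IMRT would lengthen the gap, as would cisplatin given after the last fraction, since Section 8.6 leaves cisplatin days flexible. This should be corrected, but it does not threaten the main safety conclusions.

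**What to change.** In Section 11.5, reconcile the ongoing rule and the later GC4419-only phrase with the 30-Day Follow-up Period of Section 11.2.2, so that a single date governs ongoing status, and state that stop dates are collected up to that date. While doing so, check Section 11.8.1, which attaches the same period name to a 30-day window in a sentence about GC4419 dosing.

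For any subject already past the earlier date, query whether non-serious AEs marked ongoing had resolved by the later one.

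As a side check, not a defect in the supplied text: confirm that the separate SAP derives duration per continuing clinical event, since Section 11.5 opens a new AE record at each grade change.

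The cost is two phrases in Section 11.5 and a targeted query. No visits are added, because the weekly post-IMRT visits already record AEs.
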